8.2.4. GMI Reduction

GMI is assessed at screening, Day 1, Day 3, Day 5, Day 7, Day 10, Day 14, then every 14 days during treatment, at EoT and at Follow-up.

GMI reduction at a visit will be calculated as the baseline result minus the result at the visit.

GM reduction will be summarized, by treatment, for the Intent-to-Treat Population at Week 1 (Day 7), Week 2 (Day 14), Week 4 (Day 28) and Week 6 (Day 42).

In addition, percentage reduction will also be summarized.

Note, assessment of GMI endpoints will be based on the central laboratory results. Local results will be listed only.

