AEs will be collected and evaluated from Baseline (Treatment Day 1)), after the first dose of SCY-078 and SOC voriconazole and through the end of the study. AEs will also be collected at any unscheduled visits. A general physical exam will be conducted at Screening and Baseline (Treatment Day 1), at EoT and at the 6-Week FU visit. The physical examination will include an abbreviated assessment of general appearance, skin, eyes, heart, chest and abdomen. An overall visual function assessment will also be conducted as part of the physical exam to investigate visual acuity, visual field and color perception at Screening or Baseline. This visual function assessment will be repeated at approximately Treatment Day 28 if voriconazole treatment continues beyond 28 days. Vital signs, including blood pressure (systolic and diastolic), heart rate, respiratory rate and body temperature will be measured at Screening and Baseline (Treatment Day 1), at EoT and at unscheduled visits, if applicable. Safety laboratory tests (hematology, blood chemistry and urinalysis) will be performed at Screening and Baseline (Treatment Day 1), and on Treatment Days 7 and 14, at EoT and 6-Week FU. In addition, serum transaminase levels, bilirubin levels, serum electrolytes (potassium, magnesium and calcium) and amylase and lipase should be monitored at initiation of voriconazole therapy (Day 1) and then weekly during the first month of treatment (Day 7, Day 14, around Day 21 and Day 28). Monitoring frequency of these laboratory parameters may be reduced to monthly intervals during continued use of voriconazole if no clinically significant changes are noted. All medications (including prescription and over the counter [OTC] medications, supplements, and herbal products) taken from 28 days before Screening through the EoT will be recorded on the eCRF. Only the use of antifungal medications, antibiotics for any reason or medications to treat an AE will be recorded after EoT and through the 6-Week FU visit.

Efficacy Evaluations: Efficacy will be assessed primarily in terms of Global Response, ACM and GMI decrease (GMI decrease will only be assessed for subjects with a positive serum GMI at Baseline). In addition to Global Response, clinical, mycological and radiological outcomes will also be assessed. Exploratory efficacy assessments include, among others, recurrence,

performance indicators and other serological biomarkers (β-D-glucan and *Aspergillus* PCR).

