11.0 Study Design

11.1 Overall Description of the Study

This is a multicenter, randomized, double-blind, two-arm study to evaluate the safety, tolerability, efficacy and PK of the coadministration of SCY-078 plus voriconazole compared to coadministration of SCY-078 placebo plus voriconazole in male and female subjects 18 years of age and older with probable or proven IPA as defined in Section 22.3 (adapted EORTC-MSG criteria).

The primary objective of the study is to evaluate the safety and tolerability of the coadministration of SCY-078 plus voriconazole compared to the coadministration of SCY-078 placebo plus voriconazole in the treatment of IPA. Secondary objectives include efficacy assessments based on Global Response, ACM and GMI decrease (GMI decrease will only be assessed for subjects with a serum GMI above 0 at Baseline), and PK. Being this a Phase 2 study, multiple secondary and exploratory endpoints are planned, which will be evaluated as data allow considering the limitations of the planned sample size.

Subjects must meet all study criteria to be eligible for inclusion.

This study is intended for subjects with an IPA episode that, in the investigator's judgement, requires antifungal therapy and is reasonable to expect that be adequately treated with voriconazole. Subjects with breakthrough IPA while receiving antifungal prophylaxis may be considered for enrollment if, in the investigator's judgement, the IPA episode is expected to be adequately treated with voriconazole.

The study will be conducted at approximately 30 sites globally. Approximately 90 subjects will be screened to randomize a total of approximately 60 subjects (30 subjects per group) into one of the two treatment groups of the study (SCY-078 plus voriconazole or SCY-078 placebo plus voriconazole).

Subjects will receive study treatment for the entire duration of the antifungal therapy (i.e., for a recommended minimum of 6 weeks and a maximum of 13 weeks).

The study will consist of a Screening Period (Days -4 to -1) to assess subject eligibility; a

SCYNEXIS, Inc.	IND #107,521
PROTOCOL SCY-078-206	Version 5.0

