19.7 Efficacy

19.7.1 Efficacy Assessments

Efficacy will be assessed primarily in terms of Global Response, ACM and GMI decrease (GMI decrease will only be assessed for subjects with a Serum GMI above 0 at Baseline). The DRC evaluation of Global Response is considered the key efficacy evaluation, considering the expert and independent nature of the DRC assessment. In addition to Global Response, clinical, mycological and radiological outcomes will also be assessed. Exploratory efficacy assessments include, among others, recurrence, performance indicators and other serological biomarkers (β -D-glucan and *Aspergillus* PCR).

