19.7.1.3 GMI Decrease

GMI decrease will be assessed in terms of absolute and percentage reduction relative to Baseline, and in terms of time to achieve the GMI absolute and percentage reductions. GMI decrease will be assessed in subjects with Baseline serum GMI above 0, only.

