5.2. Intent-to-Treat (ITT) Population

The ITT Population will include all randomized subject who receive at least one dose of randomized study medication. This population will be the primary population for the analysis of efficacy data. Analysis will be according to randomized treatment.

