10.7. Physical Examination

A general physical examination is done at Screening, Day 1, Day 14, Day 28, Day 42, Day 56, Day 70, Day 84, EoT and at Follow-Up.

Physical examination results will be summarized, by treatment, for the Safety Population.

11. Interim Analyses

The protocol planned for the performance of an interim analysis. However, there is no interim analysis since the study was stopped after enrolment of 22 subjects, due to patient recruitment challenges..

12. Changes from Analysis Planned in Protocol

There are currently no deviations from the analyses planned in the protocol. Enrollment into the study was stopped after 22 subjects were randomized because of the subject recruitment challenges and feasibility to enrol the planned sample size of 60 subjects.

13. Programming Considerations

All tables, figures, listings (TFLs), and statistical analyses will be generated using SAS for Windows, Release 9.4 or higher (SAS Institute Inc., Cary, NC, USA). Computer-generated table, listing and figure output will adhere to the following specifications.

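### The SAP's serum GMI and beta-D-glucan analyses omit the protocol's baseline restriction, while SAP section 12 declares no deviations

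*SAP*

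**What the plan says.** Protocol 19.7.1.3 is explicit: "GMI decrease will be assessed in subjects with Baseline serum GMI above 0, only". Protocol 11.1 ("GMI decrease will only be assessed for subjects with a serum GMI above 0 at Baseline") and 19.7.1 ("GMI decrease will only be assessed for subjects with a Serum GMI above 0 at Baseline") say the same. The synopsis, under Efficacy Evaluations, is stricter: "GMI decrease will only be assessed for subjects with a positive serum GMI at Baseline". Protocol 22.3 puts the positive cut-off for serum at 0.5.

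SAP 8.2.4 states: "GM reduction will be summarized, by treatment, for the Intent-to-Treat Population at Week 1 (Day 7), Week 2 (Day 14"), continuing to Weeks 4 and 6, with no baseline condition. SAP 8.2.5 (five target rates) and 8.2.6 (time to the same five targets) name neither a population nor a baseline condition. SAP 5.2 then governs, saying of ITT: "This population will be the primary population for the analysis of efficacy data". ITT is every randomized and dosed subject.

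For beta-D-glucan, protocol 10.3 and SAP 4.3 both qualify the target-change endpoint with a positive baseline. SAP 8.2.10 analyses it for ITT without that qualifier.

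SAP 12 nevertheless says: "There are currently no deviations from the analyses planned in the protocol".

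**The concern.** Protocol 19.7.1 places GMI decrease among the main efficacy measures: "Efficacy will be assessed primarily in terms of Global Response, ACM and GMI decrease". Protocol 8.2 says the study should guide endpoint selection for a larger Phase 3 trial. If the tables are programmed from the SAP as written, they can include subjects for whom a target is undefined, out of reach or already met at baseline. The protocol tried to prevent at least part of this. Because section 12 declares no deviations, a reader of the report would not know that the condition had been dropped.

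**Working it through.** There is no sample-size or power figure to reproduce, because both documents say none was calculated. The check is a comparison of text, followed by an illustration.

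**1. Can ITT contain subjects without a positive baseline serum GMI?** Yes.
- Protocol 22.3 accepts BAL GMI of at least 1, or cytology, microscopy, culture or PCR from lung samples, as the mycological criterion.
- Inclusion criterion 3 in protocol 12.1 asks for a serum GMI result within 96 hours, not a positive one.
- Table 4, footnote l, is stricter, but it still accepts a positive BAL sample in place of serum.
- Qualification uses local results (protocol 15.15). The endpoints use central results (SAP 8.2.4) and the last value before first dose (SAP 6.2). A subject who was serum-positive at screening can therefore have a lower analysed baseline.

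**2. Does other SAP text restore the restriction?** No. SAP 8.2.15 to 8.2.18 limit themselves to subjects with positive serum galactomannan at baseline, so the authors wrote the limit where they meant it. The MITT population (SAP 5.4) requires a positive serum GMI, but no analysis in SAP section 8 is assigned to it.

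**3. What happens by baseline value b?**

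| Baseline serum GMI | Effect on the targets | Excluded by *above 0*? | Excluded by *positive*? |
|---|---|---|---|
| b = 0 | Percent change divides by zero; no fall is possible | Yes | Yes |
| 0 < b < 0.25 | A fall of 0.25 is impossible; already below 0.5 | No | Yes |
| 0.25 ≤ b < 0.5 | Already below 0.5 | No | Yes |
| b ≥ 0.5 | All five targets are meaningful | No | No |

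Two single-subject examples with assumed values:
- From 0.40 to 0.38 is a fall of 0.02, or 0.02/0.40 = 5.0%, yet the result is below 0.5.
- From 0.20 to 0 is a fall of 0.20/0.20 = 100%, yet 0.20 is less than 0.25.

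**4. Size per subject (illustration).** SAP 3.4 gives about 11 subjects per group. Assume 10 subjects for whom the target is meaningful, x of them responding, plus one added subject.
- Added subject cannot succeed: x/11 − x/10. For x = 3, 5, 7 this is 27.3 − 30.0 = −2.7, 45.5 − 50.0 = −4.5 and 63.6 − 70.0 = −6.4 points.
- Added subject counted as success on the below-0.5 target: (x+1)/11 − x/10. For x = 3, 5, 7 this is 36.4 − 30.0 = +6.4, 54.5 − 50.0 = +4.5 and 72.7 − 70.0 = +2.7 points.

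SAP 8.2.5 introduces its list as reductions, so a baseline of 0, which cannot fall, is naturally a non-success. On that reading the positive shifts come from baselines above 0 and below 0.5.

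**5. Effect on a between-arm difference (illustration).** Suppose k of 11 subjects in each arm have the same fixed outcome whatever the treatment. A true 20-point difference then becomes 20 × (11 − k)/11, which is 16.4, 12.7 or 9.1 points for k = 2, 4 or 6. With unequal k the direction is not fixed. The documents give no value for k.

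**6. Beta-D-glucan.** A subject negative at baseline already meets the negative-result target. SAP 4.3 excludes that subject and 8.2.10 does not, so here the SAP also disagrees with itself.

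**The case against.** The strongest reply is that the departure from the protocol body is narrow. Under 19.7.1.3 only a baseline of exactly 0 is excluded. Under the table default in SAP 13.2.5.2 (subjects with an observation), such a subject would arguably drop out of the percent-change targets anyway. That leaves the absolute-reduction summary and the two absolute targets. This stands, and it limits the size of the error. It does not remove the mismatch or make section 12 correct.

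A reader might infer that every baseline below 0.5 is a departure from the protocol. It is not: *above 0* admits baselines between 0 and 0.5, and only the synopsis wording excludes them. The 0.40-to-0.38 and 0.20-to-0 examples therefore conform to the protocol body. They show a weakness in the target definitions of protocol 10.2, which SAP 4.2 repeats faithfully.

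A reader might also infer a contradiction in the denominators, because SAP 8.1 keeps subjects with missing data in the denominator as indeterminate. The documents do not support that. Section 8.1 concerns Global Response at EoT, Day 42 and Day 84, and SAP 13.2.5.2 supplies a rule for other percentages. Similarly, SAP 8.2.11 departs from nothing on PCR conversion, because the condition is part of the endpoint. Stating both denominators would be a useful but optional clarification.

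Finally, target-specific baseline limits appear nowhere in the protocol. They are an addition, needed only if *above 0* is kept, and should be recorded as such.

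**Conclusion.** The omission is real and should be corrected. SAP 8.2.4 to 8.2.6 drop a restriction that the protocol states in four places, SAP 8.2.10 drops one that the SAP itself states in 4.3, and section 12 is inaccurate on both. The protocol also gives two limits that are not interchangeable: *above 0* cures only the undefined percentages, while *positive* cures the unreachable and already-met targets as well.

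The size is unknown. The number of affected subjects is not given and may be zero. The shifts of 2.7 to 6.4 points per subject assume an arm of 11 with 3 to 7 responders among 10. It would go too far to infer that the five targets cannot be used, or that the trial's main conclusion is at risk. The planned comparison is between arms within each target, the outputs are descriptive, the primary endpoint is safety, and the key secondary endpoint is Global Response by the DRC.

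**What to change.** 1. Reconcile *above 0* with *positive* as the limit for GMI decrease, and write the agreed limit into SAP 8.2.4, 8.2.5 and 8.2.6, applied to the central baseline value.
2. Limit SAP 8.2.10 to subjects who are beta-D-glucan-positive at baseline, as in SAP 4.3.
3. If *above 0* is kept, evaluate the below-0.5 target (rate and time to target) only in subjects with central baseline serum GMI of at least 0.5, and the 0.25-fall target only in those with baseline of at least 0.25. Record these narrower limits in SAP 12.
4. If *positive* is chosen, define a serum-positive subset of ITT. MITT is close, but it also requires DRC confirmation of the diagnosis.

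The cost is SAP wording and re-specified denominators, with no new data. The drawback is smaller numbers in the biomarker tables of a study of about 22 subjects.

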8.2.5. Percentage of Subjects with Target Changes in GMI from Baseline

The percentage of subjects with the following target reductions in serum GMI from baseline will be presented at Weeks 1, 2, 4 and 6:

- Fifty percent reduction or greater
- Twenty-five percent reduction or greater
- Any percent reduction
- Reduction equal to or greater than 0.25
- Reduction to < 0.5

The difference in rates between treatments will be presented along with a 95% CI calculated using the method of Clopper-Pearson.

8.2.6. Time to Achieve Target Changes in GMI from Baseline

The following targets will be considered:

- Fifty percent reduction
- Twenty-five percent reduction
- Any percent reduction
- Reduction equal to or greater than 0.25
- Reduction to < 0.5 in 2 consecutive samples

Time to achieve a target change in serum GMI from baseline will be expressed in days and calculated using the formula:

$$\text{Time to Achieve} = \text{Date of Achievement/Censoring} - \text{Date of Randomization.}$$

Subjects not achieving the target by Day 84 will be censored at Day 84 Or date of death, or date of withdraw, or date of last GMI assessment whichever comes earliest.

The number and percentage of subjects with events and censored will be summarized.

The Kaplan-Meier method will be used to estimate the distribution of time to achieve target for each treatment group. The 25th percentile, median and 75th percentile and their 95% CIs will be presented.

8.2.7. Clinical Response, Mycological Response and Radiological Response at EoT, Day 42 and Day 84 as determined by the DRC

Clinical Response, Mycological Response and Radiological Response at EoT, Day 42 and Day 84 as determined by the DRC will be analyzed for the ITT Population as for the Global Response by the DRC, see Section 8.1.

8.2.8. Clinical Response, Mycological Response and Radiological Response at EoT, Day 42 and Day 84 as determined by Principal Investigator

Clinical Response, Mycological Response and Radiological Response at EoT, Day 42 and Day 84 as determined by Principal Investigator will be analyzed for the ITT Population as for the Global Response by the DRC, see Section 8.1.

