The largest randomized controlled study evaluating antifungal combination therapy for patients with IPA was reported by Marr K et al. in 2015.⁷ This study assessed the safety and efficacy of voriconazole and anidulafungin compared with voriconazole monotherapy for the treatment of IPA. The study included 454 patients with hematological malignancies or hematopoietic stem cell transplantation and suspected or documented IPA and the primary analysis was done in 277 patients with documented IPA. Although the study failed to demonstrate statistically significant improvement in all-cause mortality with the combination therapy when compared with monotherapy, there was a clear trend towards improved survival in the group receiving combination therapy. Overall mortality rates at 6 weeks were 19.3% (26 of 135) for combination therapy and 27.5% (39 of 142) for monotherapy (difference, - 8.2 percentage points [95% CI, - 19.0 to 1.5]; P = 0.087).

Most patients (218 of 277 [78.7%]) had a diagnosis of IPA established by radiographic findings and mycological evidence in the form of galactomannan positivity. In a post hoc analysis of this dominant subgroup, 6-week mortality was lower in combination therapy than in monotherapy (15.7% [17 of 108] vs. 27.3% [30 of 110]; difference, -11.5 percentage points [CI, -22.7 to -0.4]; P= 0.037). A limitation of this study was that anidulafungin is only available intravenously (IV), thus limiting its use for long-term administration as often needed in IPA patients, resulting in a median duration of the combination therapy of 14 days.

SCY-078 antifungal activity

The spectrum and potency of activity of SCY-078 has been evaluated by numerous independent laboratories against an extensive panel of clinically relevant yeast and mold isolates using the Clinical and Laboratory Standards Institute (CLSI) and European Committee on Antimicrobial Susceptibility Testing (EUCAST) methods. Overall, the epidemiological studies have demonstrated that SCY-078 has potent, broad-spectrum activity against the majority of the clinical isolates tested. These studies have laid the foundation in support of the use of SCY-078 for the treatment of invasive fungal infections.

In vitro activity against Candida spp.

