3.4. Brief Description

This is a multicenter, randomized, double-blind, two-arm study to evaluate the safety, tolerability, efficacy and PK of the coadministration of ibrexafungerp plus voriconazole compared to coadministration of ibrexafungerp placebo plus voriconazole in male and female subjects 18 years of age and older with probable or proven IPA.

The study will be conducted at approximately 30 sites globally (revised to 8 number of sites with subjects randomized). Approximately 90 subjects will be screened to randomize a total of approximately 60 subjects (revised

to approximately 22 subjects randomized , 11 subjects per group) into one of the two treatment groups of the study (ibrexafungerp plus voriconazole or ibrexafungerp placebo plus voriconazole).

Subjects will receive study treatment for the entire duration of the antifungal therapy (i.e., for a recommended minimum of 6 weeks and a maximum of 13 weeks).

The study will consist of a Screening Period (Days -4 to -1) to assess subject eligibility; a Baseline visit (also considered Treatment Day 1) to confirm subject eligibility and begin study treatment; additional scheduled treatment visits (Treatment Days 3, 7, 10, 14 and treatment visits every 14 days thereafter until the EoT) to perform safety, tolerability, efficacy and PK assessments, an EoT visit to assess efficacy outcomes, a Follow-up (FU) visit 6 weeks after EoT (6-Week FU) to assess recurrence and safety, and 2 survival visits/contacts to determine survival status and treatment outcome. The Screening Period and Baseline visit may be combined for certain subjects. Unscheduled visits may also be conducted as needed.

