8.2.13. Time to Achieve a 10-Point Improvement in Karnofsky Score from Baseline

Time to achieve a 10-point improvement in Karnofsky score from baseline will be expressed in days and calculated using the formula:

$$\text{Time to Achieve} = \text{Date of Achievement/Censoring} - \text{Date of Randomization.}$$

Subjects not achieving the 10-point improvement by Day 84 will be censored at their last Karnofsky assessment date, date of withdraw, date of death or at Day 84 whichever comes first.

The number and percentage of subjects with events and censored will be summarized.

The Kaplan-Meier method will be used to estimate the distribution of time to achieve target for each treatment group. The 25th percentile, median and 75th percentile and their 95% CIs will be presented.

8.2.14. Percentage of Subjects with a Recurrence of the Baseline Fungal Infection within 42 Days (Week 6) after EoT

Assessment of recurrence of the baseline fungal infection will take place at the follow-up visit, 6 weeks after EoT.

The percentage of subjects with a recurrence will be summarized, by treatment, for the ITT Population. The denominator for the percentage will be the number of subjects without the baseline fungal infection at EoT.

8.2.15. Relationship Between Serum GMI Decrease and ACM at Days 42 and 84 for subset of patients with positive serum galactomannan at baseline

At Day 42, subjects will be categorized as dead or alive. For each of these two groups of subjects, a boxplot will be presented showing their last available GMI decrease, up to and including Day 42. Should a subject have no post baseline GMI data then they will not be included in the plot. The plot will be based on the ITT Population.

The above plot will be repeated for Day 84.

8.2.16. Relationship between serum GMI decrease and global response at D42 and EOT for subset of patients with positive serum GM at baseline**8.2.17. Relationship between serum GMI decrease and clinical response at D42 and EOT for subset of patients with positive serum GM at baseline****8.2.18. Relationship between serum GMI decrease and radiological response at D42 and EOT for subset of patients with positive serum GM at baseline****8.2.19. Number of subjects with complete response and alive at Day 42 and at Day 84****8.2.20. Days of Hospital Stay and Days of ICU Stay**

For each subject the number of days of hospital stay and the number of days of ICU stay will be calculated.

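### Time to GMI target and time to Karnofsky improvement censor deaths under Kaplan-Meier, so the curves overstate achievement and the quartiles are too short when deaths precede later achievements

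*SAP*

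**What the plan says.** SAP 8.2.6 covers five serum GMI targets, all listed as secondary endpoints in SAP 4.2. Its censoring rule begins "Subjects not achieving the target by Day 84 will be censored at Day 84 Or date of death" and, after adding withdrawal, ends "or date of last GMI assessment whichever comes earliest". The estimator follows: "The Kaplan-Meier method will be used to estimate the distribution of time to achieve target for each treatment group", with the 25th, 50th and 75th percentiles and their 95% confidence intervals. Alongside these, "The number and percentage of subjects with events and censored will be summarized".

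SAP 8.2.13 covers the 10-point Karnofsky improvement, an exploratory endpoint in SAP 4.3: "Subjects not achieving the 10-point improvement by Day 84 will be censored at their last Karnofsky assessment date, date of withdraw, date of death". The earliest of these dates applies, with Day 84 as the upper limit. Kaplan-Meier and the same three percentiles are used.

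For these six endpoints neither document gives a competing-risk method, a rule that counts death as non-achievement, or a sensitivity analysis. No between-arm test is specified for them.

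**The concern.** Kaplan-Meier treats a censored subject as one who would go on to reach the target at the same rate as those still under observation. That is reasonable for someone who stops being sampled while alive, but it cannot hold for someone who has died. The probability belonging to the dead is passed to the survivors, so one minus Kaplan-Meier overstates the proportion reaching the target and its percentiles come too early.

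Elsewhere the documents treat death as an outcome. It is a separate Global Response category that cannot count as a response (SAP 14.1), and it scores 0 on the Karnofsky scale (Protocol Appendix D). In SAP 8.2.13 the worst value on that scale is therefore handled as unknown.

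Mortality is itself a secondary efficacy endpoint, so the distortion can differ between arms. Protocol 19.1 names preliminary effect sizes for all the efficacy endpoints as the main goal, and Protocol 8.2 expects the results to guide the choice of Phase 3 endpoints. A misleading GMI time would feed into both.

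**Working it through.** **Inputs from the documents**
- Censoring rules and estimator: SAP 8.2.6 and 8.2.13.
- Arm size: "approximately 22 subjects randomized , 11 subjects per group" (SAP 3.4).
- GMI sampling after Day 1: "Day 3, Day 5, Day 7, Day 10, Day 14, then every 14 days during treatment, at EoT and at Follow-up" (SAP 8.2.4).
- Mortality: "Overall mortality rates at 6 weeks were 19.3% (26 of 135) for combination therapy and 27.5% (39 of 142) for monotherapy" (Protocol 8.1, a cited combination trial). The fractions agree: 26/135 = 0.193 and 39/142 = 0.275. On 11 subjects they are 11 × 0.193 = 2.1 and 11 × 0.275 = 3.0 deaths.

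**Assumed.** The documents give no expected time to any target, so I assume a cause-specific median of 14 or 28 days with constant hazards. The event days in step 2 are also assumed. There is no planned figure to reproduce.

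**Step 1: effect on the planned percentiles within an arm**

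Death hazard: λd = −ln(1 − 0.275)/42 = 0.00766 per day. Target hazard with a 14-day median: λt = ln 2/14 = 0.04951 per day.
- Kaplan-Meier with deaths censored: t(p) = −ln(1 − p)/λt.
- Cumulative incidence: F(t) = [λt/(λt + λd)] × [1 − exp(−(λt + λd)t)], so t(p) = −ln[1 − p(λt + λd)/λt]/(λt + λd).

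Here λt + λd = 0.05717 and (λt + λd)/λt = 1.1547. The true median is −ln(1 − 0.5773)/0.05717 = 15.1 days.

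| Assumed median | Percentile | Kaplan-Meier (days) | Cumulative incidence (days) |
|---|---|---|---|
| 14 days | 25th | 5.8 | 6.0 |
| 14 days | 50th | 14.0 | 15.1 |
| 14 days | 75th | 28 | 35 |
| 28 days | 50th | 28 | 33 |
| 28 days | 75th | 56 | not reached by Day 84 (F = 71.4%) |

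At 19.3% mortality and a 14-day median, the median is 14.0 against 14.7 days.

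In this model the Kaplan-Meier formula contains only λt. Two arms with the same λt get the same Kaplan-Meier curve whatever their mortality. Step 1 therefore shows bias within an arm, not a difference between arms.

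**Step 2: deaths concentrated among non-achievers, 11 per arm**

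Six subjects achieve the target, on Days 7, 10, 14, 14, 28 and 42. Five never do.
- *No deaths, all five sampled to Day 84.* The curve ends at 6/11 = 54.5%. The proportion not achieved is 6/11 after Day 28 and 5/11 after Day 42, so the median is Day 42.
- *Three of the five die, on Days 5, 8 and 12.* Risk sets at the event days are 10, 8, 6, 4 and 3. Not achieved: 9/10 × 7/8 × 4/6 × 3/4 × 2/3 = 0.2625. The curve ends at 73.8%. It passes 50% on Day 28 (47.5% after Day 14, 60.6% after Day 28).
- *Same three deaths as a competing event.* The cumulative incidence is 6/11 = 54.5% with median Day 42, identical to the arm without deaths.
- *Three deaths after Day 42.* Kaplan-Meier stays at 54.5% and Day 42.

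**Step 3: the last-assessment clause**

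If the three who died are censored at their last samples on Days 5, 7 and 10, the risk sets are again 10, 8, 6, 4 and 3, and the curve again ends at 73.8%. Removing the date of death from the rule would change nothing here.

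**The case against.** A reader might infer more than the documents support, in three ways.

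*That the comparison of arms will reverse.* An example can be built. Five achievers (Days 7, 10, 14, 14 and 28) with four early deaths leave risk sets of 9, 7, 5 and 3. Kaplan-Meier then ends at 1 − 8/9 × 6/7 × 3/5 × 2/3 = 69.5% with median Day 14. This looks better than 6/11 with no deaths (54.5%, Day 42), although true achievement is 45.5%. But it needs 4 of 11 early deaths against none, whereas the cited rates imply about 3 against 2. With the six achievers of step 2 and deaths on Days 5 and 12 only, not achieved is 9/10 × 8/9 × 5/7 × 4/5 × 3/4 = 0.343. The curve ends at 65.7% with median Day 28, the same median as with three deaths. Reversal is possible, not expected.

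*That the SAP will publish grossly inflated success percentages.* Kaplan-Meier percentages at Days 42 and 84 are planned only for overall survival (SAP 8.2.2). The planned outputs here are percentiles and the crude event count, which is not inflated: it reads 6/11 in every step 2 scenario. Deaths are also shown separately (SAP 8.2.2 and 8.2.3).

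*That a trial conclusion is invalid.* These are descriptive endpoints without a test. The primary endpoint is safety, and the key efficacy endpoint counts death as a non-response. GMI decrease is assessed only in subjects with baseline serum GMI above 0 (Protocol 19.7.1.3), so fewer than 11 per arm may contribute.

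All of this limits the consequence. None of it makes the estimator right: a correct crude count beside the quartiles does not correct the quartiles.

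**Conclusion.** The analysis is wrong as written for all six endpoints and should be corrected, but it does not undermine the trial's main conclusions. In the constant-hazard case with a 14-day median, the first quartile hardly moves, the median moves by about a day and the 75th percentile by about a week. With a 28-day median, the median moves by about 5 days, and a 75th percentile of 56 days would be reported where the true one is not reached by Day 84.

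That the arm with more early deaths is flattered depends on deaths falling mainly among non-achievers and before later achievements. The step 2 contrast also assumes that surviving non-achievers keep being sampled. If three survivors had their last GMI on Days 5, 7 and 10, Kaplan-Meier would give 73.8% for them too. That would be ordinary censoring of living subjects, a separate matter. The documents do not support a claim that the order of the arms will reverse.

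**What to change.** In SAP 8.2.6 and 8.2.13:
- Treat death before the target, up to Day 84, as a competing event, including for subjects whose last assessment precedes death.
- Censor only subjects who are alive, at withdrawal, last assessment or Day 84.
- Report the Aalen-Johansen cumulative incidence by arm with 95% confidence intervals, and take the percentiles from that curve, shown as not reached where that applies.

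Keeping the dead in the risk set to Day 84 as non-achievers gives exactly the same answer only when nobody else is censored earlier. Living subjects may be censored early here, so it should not be offered as an equivalent.

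The cost is two short SAP edits and less favourable displayed times. No new data are needed, since date of death is already collected (Protocol 15.23).
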